3.1. Primary Objective

The primary objective is to test the hypothesis that a once-weekly injection of 1.5 mg dulaglutide reduces the occurrence of the composite primary endpoint of death from cardiovascular (CV) causes, nonfatal myocardial infarction (MI), or nonfatal stroke when added to the glucose-lowering regimen of patients with type 2 diabetes, compared to the addition of a once-weekly placebo injection.

3.2. Secondary Objectives

3.2.1. Efficacy Objectives

The secondary efficacy objectives are to assess the effects of add-on therapy with 1.5-mg dulaglutide compared to placebo on the occurrence of:

- the composite microvascular endpoint of diabetic retinopathy requiring laser therapy, vitrectomy, or anti-vascular endothelial growth factor (VEGF) therapy; development of clinical proteinuria, a 30% decline in estimated glomerular filtration rate (eGFR), or need for chronic renal replacement therapy
- hospitalization for unstable angina
- each component of the composite primary endpoint
- all-cause mortality
- heart failure (HF) requiring hospitalization or an urgent HF visit

3.2.2. Prespecified Safety Objectives (Adverse Events of Special Interest)

The prespecified safety objectives are to assess the effects of add-on therapy with 1.5 mg dulaglutide compared to placebo on the incidence of:

- acute pancreatitis
- serious gastrointestinal (GI) events
- any cancer (excluding basal or squamous cell skin cancer) and specific categories of
 - pancreatic cancer
 - medullary thyroid carcinoma (MTC) and C-cell hyperplasia
 - thyroid carcinomas
- severe hypoglycemia

- immune mediated reactions including serious allergic and hypersensitivity reactions
- serious hepatic events
- clinically significant supraventricular arrhythmias and cardiovascular conduction disorders
- serious renal events
- discontinuation of study drug for any reason

3.2.3. Additional Objectives

The additional objectives are to assess the effects of 1.5 mg dulaglutide compared with placebo on the following:

- hemoglobin A1c (HbA1c) levels
- weight
- waist/hip ratio
- the composite endpoint of death from CV causes, nonfatal MI, nonfatal stroke, or hospitalization for unstable angina
- coronary, carotid, or peripheral revascularizations, individually and compositely
- any hospitalization
- cognitive function as measured by the Montreal Cognitive Assessment (MoCA) and the Digit Symbol Substitution Test (DSST)
- erectile function using the International Index of Erectile Function Questionnaire (IIEF)
- any fracture
- development of cholelithiasis

4. A Priori Statistical Methods

REWIND will be a randomized, double-blind, placebo-controlled, international, multicenter, parallel-arm trial to determine whether the addition of the once weekly glucagon-like peptide-1 (GLP-1) analog dulaglutide to the diabetes regimen of patients with type 2 diabetes at high CV risk reduces major adverse CV and other serious outcomes. There will be a single-blind placebo run-in period to test a prospective participant's behavior and willingness to inject study drug on a weekly basis, given that patients will be expected to inject study therapy for 5 or more years.

There will be 1 interim analysis and 1 final analysis. The interim analysis will be performed when approximately 61% (730 events) of the positively adjudicated primary endpoint events have occurred. The final analysis will be performed at 100% (approximately 1200) of the positively adjudicated primary endpoint events, if the study is not stopped early. At the interim analysis time point (Figure GBDJ.4.1), superiority will be tested first; if successful, the trial may stop and superiority will be declared. Otherwise, the trial will continue to the end, where, at 1200 events, superiority will be tested followed by noninferiority. The interim and final analyses will be performed on unblinded study data by the Independent Data Monitoring Committee (IDMC) that will use the results and the foregoing decision rules as guidelines. Thus, if the interim analysis shows clear benefit of dulaglutide over placebo for the primary endpoint, the IDMC may recommend early termination of the study. Alternatively, if the boundaries are crossed at the interim analysis, the IDMC may still recommend the trial continue and not stop for early efficacy. At any time during the trial, the IDMC could recommend stopping the trial for safety reasons. The alpha used across the analyses will be monitored by an O'Brien-Fleming spending function (O'Brien and Fleming 1979; Jennison and Turnbull 2000), (for example, with 730 events at the interim, 2-sided alpha = 0.008; power 51.3%). The alpha used at the final analysis will be adjusted to maintain the overall type I error control at a 2-sided significance level of 0.05. This will be accomplished using EAST software to calculate the alpha level for the final analysis considering the actual amount of information at the interim analysis (for example, with 1200 events at the final analysis, 2-sided alpha = 0.048; overall power = 92.8%). At the final analysis, superiority will be tested followed by noninferiority. The adjusted 95% confidence interval (CI) for the hazard ratio will be calculated.

[figure not shown]

Figure GBDJ.4.1. Interim decision rule.

The median unbiased estimator for the hazard ratio will be reported if the trial is stopped early for efficacy at an interim analysis.

4.1. Determination of Sample Size

For the initial powering of the trial, a minimum of 1067 unique primary endpoint events will be required to provide 90% power to demonstrate the superiority of dulaglutide over placebo at a true hazard ratio of 0.82 and 2-sided significance level of 0.05. To calculate the sample size, the following assumptions were used and yielded a sample size requirement of approximately 9600 patients: (1) two-sided significance level of 0.05; (2) 90% power for the primary endpoint; (3) patient accrual over 3 years; (4) annual placebo group event rate of 2.0% for the primary endpoint; (5) maximum duration of follow-up of 8 years; (6) a detectable hazard ratio of 0.82 between dulaglutide and placebo in terms of the primary endpoint; and (7) annual dropout rate of 0.15%.

The calculations were performed using nQuery Advisor® Version 7.0. This software provides sample size estimates for tests based on exponential survival, accrual period and dropouts. The sample size and other trial characteristics, such as interim analysis power, were also assessed through trial simulation. Trial assumptions were based on information from the scientific leadership of the study and a review of the relevant literature.

4.2. General Considerations

All entered data will be verified, and archived at a contract research organization (CRO) external to Lilly and/or at Lilly. An independent statistical analysis center (ISAC) will perform analyses for the IDMC prior to unblinding. After database lock at the conclusion of the study, analyses for the major key manuscripts will be conducted by the same or another ISAC based on data supplied by the CRO and the relevant manuscripts will be prepared by a writing group chosen by the Operations Committee. Data listings, summaries, and analyses will also be performed by the CRO and/or by Lilly for the purpose of the final clinical study report (CSR).

Efficacy and safety analyses will be conducted using the intent-to-treat (ITT) population. This population will include all randomized patients within the treatment group the patients were assigned to regardless of whether or not they took study drug or the correct study drug. A patient is considered randomized once the call has been made to interactive voice response system (IVRS) and a treatment is assigned at Visit 3.

Additional analyses will be conducted using the per-protocol (PP) population. The PP population is a subset of the ITT population defined as all randomized patients who have not permanently discontinued study drug, discontinued from the study, have an overall adherence of $\geq 75\%$, and have no important protocol deviations. The primary efficacy analysis will be repeated using the PP population. Important protocol deviations are defined in Section 4.7.

The analysis populations used in this study are defined in [Table 4.1](#).

Unless otherwise specified, listings will be conducted using all randomized patients. The data collected will be presented as listings by investigator site, patient, and treatment.

Unless otherwise noted, all tests of treatment effects will be conducted at a 2-sided alpha level of 0.05 and CIs will be calculated at a 2-sided 95% confidence level. A graphical approach for multiple comparisons (Bretz et al. 2009; Bretz et al. 2011) will be used to strongly control the overall Type I error (2-sided alpha of 0.05) for testing the null hypothesis of no treatment effect with respect to the secondary endpoints.

For subgroup analyses, all tests of interactions between treatment groups and other factors will be conducted at a nominal 2-sided alpha level of 0.10 and will be deemed to be exploratory. No adjustment for multiplicity will be performed unless otherwise specified.

Countries in similar geographic regions with <10 patients will be pooled in order to achieve a pooled country of at least 10 patients. All analyses using country in the model will use pooled country, unless otherwise specified. The final pooling by country and geographic region will be specified prior to data lock.

The baseline is Visit 3. If baseline data are missing, the last measurement taken prior to this visit will be used for the baseline measurement.

The primary analysis and key secondary CV endpoint analyses will be based on adjudicated events that occurred after randomization (Visit 3). Sensitivity analyses may be conducted

including events reported by investigators or events identified through safety reviews, to assess their impact on the primary analysis results.

All analyses will be implemented using SAS Version 8.2® or higher.

4.3. Default Analysis Methods

A default analysis method will be defined for certain types of variables (for example, baseline continuous, baseline categorical and time-to-event) that will be commonly encountered in this study. If a specific analysis requires a methodology other than the default for that variable type, the methodology will be described in the appropriate sections of this SAP.

4.3.1. Baseline Analyses

Measurements collected at Visit 3 will be considered the baseline values. If data from Visit 3 are missing, measurements from the screening/run-in period (between Visit 1 and Visit 3) will be used. If a patient has no information for a variable prior to randomization, data will not be imputed and the patient will not be included in the analysis. Baseline analysis for any particular variable will be conducted using all randomized patients with baseline data for that variable.

The default analysis method for continuous baseline variables will be an ANOVA model with only a fixed effect for treatment; however, in situations where the baseline variable will be expected to violate the assumption of normality, Wilcoxon's rank sum test will be used. Such situations will be appropriately identified throughout this SAP. Summaries for continuous variables will include descriptive statistics (that is, number of patients, mean, standard deviation (SD), sample size, median, 10th percentile, 90th percentile, and interquartile range).

Categorical variables will be compared between treatments using Pearson's chi-square test if the expected count is at least 5 in at least 80% of the cells; otherwise, Fisher's exact test will be used. Summary statistics for categorical variables will include sample size, number, and proportion of patients.

For the CSR, a baseline factor will be considered as a covariate for a covariate-adjusted analysis only if the baseline factor is both clinically and statistically significantly different between treatment groups.

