4.3.5.2. Exploratory Subgroup Analyses

To select additional factors for subgroup analyses, clinically relevant baseline characteristics will be identified for the primary outcome variable and each of its components. A Cox proportional hazards regression model adjusted for baseline risk factors will be obtained using a model selection process, guided by clinical review of the published literature. All these factors will be forced into the model, along with the above prespecified subgroup variables. For all factors, the significance level for remaining in the model will be 0.05. After the selection of terms into the model concludes, treatment will be added to the model. For all dichotomous terms in the final model, parameter estimates, standard errors and p-values plus the hazard ratio and its 95% CI will be reported.

Any factors remaining in the final proportional hazards model will also be used for subgroup analyses.

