4.13.3. Subgroup Analysis of Primary Endpoint

The effects of dulaglutide compared to placebo on the incidence of the composite primary endpoint events will be examined across the prespecified subgroups of interest listed in Section 4.3.5.

The clinically relevant baseline characteristics for exploratory subgroup analyses for the primary endpoint include: prior MI, prior history of stroke or transient ischemic attack (TIA), prior hospitalization for unstable angina, prior coronary revascularization, existing microalbuminuria (defined as a urine albumin/creatinine ratio (ACR) >30 mg/g and ≤300 mg/g) or macroalbuminuria (see Section 4.17.3), current smoker, hypertension, hyperlipidemia, aspirin use, beta-blocker use, calcium channel blocker use, ACE inhibitor or angiotensin receptor blocker use, diuretic use, and antithrombotic (nonaspirin antiplatelets, vitamin K antagonists, heparin, direct thrombin inhibitor, or other antithrombotics).

A risk-adjusted analysis will be performed using these baseline characteristics, the prespecified subgroups, and a multifactor proportional hazards model. The baseline characteristics remaining in the final multifactor proportional hazards model plus the prespecified subgroup variables will be used for subgroup analyses.

The risk-adjusted and subgroup analyses will be performed using the ITT population.

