4.14.2.2. Subgroup Analysis of Nonfatal Myocardial Infarction Endpoint

For subgroup analyses all adjudicated nonfatal MI outcomes will be included, and the analyses will be performed for the ITT population. The potentially clinically relevant baseline risk factors and medication use for exploratory subgroup analyses for the MI events will include: prior MI, prior hospitalization for unstable angina, prior coronary revascularization, current smoker, hypertension, hyperlipidemia, aspirin use, beta-blocker use, calcium channel blocker use, ACE inhibitor or angiotensin receptor blocker use, diuretic use, and antithrombotic use (excluding aspirin).

The risk-adjusted analysis will be performed using these risk factors, medication use, the prespecified subgroups (Section 4.13.3), and a multivariate proportional hazards model. The risk factors and medication use remaining in the final model plus the pre-specified subgroup variables will be used for subgroup analyses.

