4.14.4. Subgroup Analysis of Nonfatal Stroke Endpoint

For subgroup analyses all adjudicated nonfatal stroke outcomes will be included, and the analyses will be performed for the ITT population. The potentially clinically relevant baseline risk factors and medication use for exploratory subgroup analyses for the stroke events will include: prior MI, prior hospitalization for unstable angina, prior history of stroke or TIA, carotid or other artery disease, current smoker, alcohol abuse, hypertension, hyperlipidemia, aspirin use, beta-blocker use, calcium channel blocker use, ACE inhibitor or angiotensin receptor blocker use, diuretic use, history of atrial fibrillation, and antithrombotic use (excluding aspirin).

The risk-adjusted analysis will be performed using these risk factors and the prespecified subgroups, and a multivariate proportional hazards model. The risk factors and medication use remaining in the final model plus the prespecified subgroup variables will be used for subgroup analyses.

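### Does the SAP's rule that CSR covariates must differ between arms clash with the risk-adjusted models it plans elsewhere?

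*SAP*

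**What the plan says.** The last sentence of SAP 4.3.1 (Baseline Analyses) restricts adjustment in the CSR: a factor is to be "considered as a covariate for a covariate-adjusted analysis only if the baseline factor is both clinically and statistically significantly different" across the two arms. It gives no test level and no clinical threshold.

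The exploratory risk model is built differently in SAP 4.3.5.2. Candidates come from clinical review, and "All these factors will be forced into the model, along with the above prespecified subgroup variables". The next sentence reads "For all factors, the significance level for remaining in the model will be 0.05", and then "After the selection of terms into the model concludes, treatment will be added to the model".

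Three endpoint sections use this machinery without requiring imbalance:

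- Primary endpoint, 4.13.3: "A risk-adjusted analysis will be performed using these baseline characteristics, the prespecified subgroups, and a multifactor proportional hazards model".
- Nonfatal MI, 4.14.2.2: "The risk-adjusted analysis will be performed using these risk factors, medication use, the prespecified subgroups (Section 4.13.3), and a multivariate proportional hazards model".
- Nonfatal stroke, 4.14.4: "The risk-adjusted analysis will be performed using these risk factors and the prespecified subgroups, and a multivariate proportional hazards model".

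The Fine and Gray analysis in 4.14.7 also takes the 4.13.3 risk factors as covariates.

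Three further provisions bear on the point. SAP 4.3 says that where an analysis needs something other than the default, "the methodology will be described in the appropriate sections of this SAP". SAP 4.3.5 labels all subgroup and risk-adjusted work exploratory. SAP 4.13.1 sets the primary model as Cox with treatment alone.

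**The concern.** A rule that admits covariates only when the arms differ is poor practice. Under 1:1 randomization any baseline difference is chance, so the rule ignores how strongly a factor predicts outcome. It also cannot be applied until baseline data have been seen by arm. Read literally, it would keep balanced but prognostic factors out of every adjusted analysis in the CSR, while 4.13.3, 4.14.2.2 and 4.14.4 bring such factors in.

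The SAP does not settle which rule wins. Section 4.2 separates CSR analyses from manuscript analyses, but the risk-adjusted sections do not say which they serve. Section 4.3.5.2 adds its own ambiguity: factors are forced in, yet all must pass 0.05 to stay.

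At stake would be the adjusted hazard ratio offered in support of the primary result. Its covariates might be almost none, or whichever factors survive selection, and a reader could not tell in advance which.

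**Working it through.** No figure in the plan rests on this point, so there is none to reproduce. The check has three parts.

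**1. Do the passages conflict?**

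- 4.3.1 belongs to 4.3, Default Analysis Methods, and 4.3 allows specific sections to depart from the defaults. Sections 4.13.3, 4.14.2.2, 4.14.4 and 4.14.7 are such sections.
- Taken as a universal bar, 4.3.1 would exclude the baseline value from the default repeated-measures model in 4.3.2 and pooled country from the severe hypoglycemia model in 4.17.1.1. That cannot be intended.
- The Version 3 revision history lists the covariate criterion separately from the prior-CV-event variable added for multifactor-adjusted analyses. This suggests two kinds of analysis, not one rule replacing the other.
- In 4.3.5.2, forced in and then retained at 0.05 reads naturally as backward elimination from a full model. The endpoint sections support this by speaking of factors that remain in the final model.

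**2. What would each rule admit?**

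Inputs: about 9600 patients at 1:1, so 4800 per arm (SAP 4.1, 4.4); 1200 events (SAP 4); 14 factors in 4.13.3 plus 7 in 4.3.5.1, so 21 candidates. The 0.05 level for baseline comparisons is assumed, because 4.2 sets it only for tests of treatment effects.

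*Imbalance rule.* SE of a standardized difference = sqrt(2/4800) = 0.0204, so significance needs 1.96 × 0.0204 = 0.040 SD.

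- On the statistical condition alone, 21 × 0.05 = 1.05 factors pass by chance (0.21 at level 0.01; 2.1 at 0.10).
- The clinical condition must hold too. If it means 0.05 SD (assumed), P = 0.0143 and 21 × 0.0143 = 0.30 factors.
- If it means 0.10 SD (assumed), P = 9.6e-7 and the expected number is 0.00002.

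With a clinical threshold of that size, the rule usually admits nothing and leaves the treatment-only model.

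*Retention at 0.05.* For a binary factor with 30% prevalence (assumed), z = sqrt(1200 × 0.3 × 0.7) × ln(HR) = 15.87 × ln(HR).

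| Factor HR (assumed) | z | P(retained) |
|---|---|---|
| 1.10 | 1.51 | 33% |
| 1.15 | 2.22 | 60% |
| 1.20 | 2.89 | 82% |
| 1.30 | 4.16 | 98.6% |

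The two rules would therefore usually give different covariate sets.

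**3. Does the choice of set move the treatment estimate?**

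A simulation used 600 trials of 9600 patients, about 1200 events and a true treatment HR of 0.85. It had 21 independent binary factors at 30% prevalence: 5 at HR 1.25, 6 at 1.15 and 10 at 1.0, all assumed. Factors were eliminated backward at 0.05, and treatment was added afterwards.

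- Factors kept: median 9 (2.5th to 97.5th percentile 6 to 12).
- Mean log-HR: unadjusted -0.1624, fixed list of the 11 prognostic factors -0.1634, selected set -0.1632. The first two correspond to HR 0.850 and 0.849.
- SD of the paired difference, selected minus fixed: 0.0018.
- SE of the log-HR: 0.058, in line with 2/sqrt(1200) = 0.0577.

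The shift from selecting rather than fixing covariates is about 0.0018/0.058 = 3% of one standard error.

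**The case for a change.** The strongest case for a change is prespecification. In the simulation above, all 11 prognostic factors were kept together in only 4.7% of trials, and no single covariate set appeared in more than 2.2%. Selection is not needed for stability either: the 21 factors use 24 or 25 parameters, and 1200/25 = 48 events per parameter. A fixed list would cost one Cox model and no protocol amendment.

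The instability figures depend on the assumed effects. Six factors at HR 1.15 alone give 0.602^6 = 4.8% for keeping all six. If all 11 have HR 1.30, the same formula gives 0.9863^11 = 86% for keeping all of them, and 0.86 × 0.95^10 = 51% for choosing exactly that set.

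More important, an unstable covariate list did not produce an unstable treatment estimate. The candidates are named, the threshold is stated, and treatment enters only after selection, so the list cannot be steered by the treatment result. That is an acceptable exploratory procedure.

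Two parts of the objection stand. Admitting covariates by observed imbalance is a weak principle. The SAP also leaves unsaid whether 4.3.1 reaches the later sections, because the exception in 4.3 speaks of variable types rather than covariate choice.

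**Conclusion.** No change is needed. This is a gap in wording that an analyst would fill sensibly: the specific sections govern their own models, and 4.3.1 covers any further adjustment for the CSR. The primary test, its type I error, its power and the noninferiority comparison all use the treatment-only model and are untouched. The SAP already calls the affected analyses exploratory.

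A fixed covariate list would make the supportive hazard ratio more predictable in form. It would not reduce bias or add power to the primary test, and the value would move by about 3% of a standard error.

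That size rests on independent binary factors of modest strength. A stronger risk score would separate adjusted from unadjusted estimates somewhat more, since the adjusted hazard ratio is conditional. Even so, the unadjusted analysis would remain the basis for the trial's conclusion.
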